### **5.4.3 Reporting Requirements for Pregnancies**

#### **5.4.3.1 Pregnancies in Female Patients**

Female patients of childbearing potential will be instructed to immediately inform the investigator if they become pregnant during the study or within 6 months after the last doses of study drug. A Pregnancy Report eCRF should be completed by the investigator within 24 hours after learning of the pregnancy and submitted via the EDC system. A pregnancy report will automatically be generated and sent to Roche Safety Risk Management. Pregnancy should not be recorded on the Adverse Event eCRF. The investigator should discontinue vemurafenib and counsel the patient, discussing the risks of the pregnancy and the possible effects on the fetus. Monitoring of the patient should continue until conclusion of the pregnancy.

In the event that the EDC system is unavailable, a Pregnancy Report worksheet and Pregnancy Fax Coversheet should be completed and faxed to Roche Safety Risk Management or its designee within 24 hours after learning of the pregnancy with use of the fax numbers provided to investigators (see "Protocol Administrative and Contact Information & List of Investigators").

#### **5.4.3.2 Pregnancies in Female Partners of Male Patients**

Male patients will be instructed through the Informed Consent Form to immediately inform the investigator if their partner becomes pregnant during the study or within 6 months after the last dose of vemurafenib. A Pregnancy Report eCRF should be completed by the investigator within 24 hours after learning of the pregnancy and submitted via the EDC system. Attempts should be made to collect and report details of the course and outcome of any pregnancy in the partner of a male patient exposed to study drug. *When permitted by the site, pregnant partner would need to sign an Authorization for Use and Disclosure of Pregnancy Health Information to allow for follow-up on her pregnancy. If the authorization has been signed, the investigator should update the Pregnancy Report eCRF with additional information on the course and outcome of the pregnancy.* An investigator who is contacted by the male patient or his pregnant partner may provide information on the risks of the pregnancy and the possible effects on the fetus, to support an informed decision in cooperation with the treating physician and/or obstetrician.

In the event that the EDC system is unavailable, reporting instructions provided in Section 5.4.3.1 should be followed.

#### **5.4.3.3 Abortions**

Any spontaneous abortion should be classified as a serious adverse event (because the Sponsor considers spontaneous abortions to be medically significant events), recorded on the Adverse Event eCRF, and reported to the Sponsor within 24 hours after learning of the event (see Section 5.4.2).

#### **5.4.3.4 Congenital Anomalies or Birth Defects**

Any congenital anomaly or birth defect in a child born to a female patient (or female partner of a male patient exposed to vemurafenib) should be classified as a serious adverse event, recorded on the Adverse Event eCRF, and reported to the Sponsor within 24 hours after learning of the event (see Section 5.4.2).

### **5.5 FOLLOW-UP OF PATIENTS AFTER ADVERSE EVENTS**

#### **5.5.1 Investigator Follow-Up**

The investigator should follow each adverse event until the event has resolved to baseline grade or better, the event is assessed as stable by the investigator, the patient is lost to follow-up, or the patient withdraws consent. Every effort should be made to follow all serious adverse events considered to be related to study drug or trial-related procedures until a final outcome can be reported.

During the study period, resolution of adverse events (with dates) should be documented on the Adverse Event eCRF and in the patient's medical record to facilitate source data verification.

All pregnancies reported during the study should be followed until pregnancy outcome.

#### **5.5.2 Sponsor Follow-Up**

For serious adverse events, non-serious adverse event of special interest, and pregnancies, the Sponsor or a designee may follow up by telephone, fax, electronic mail, and/or a monitoring visit to obtain additional case details and outcome information (e.g., from hospital discharge summaries, consultant reports, autopsy reports) in order to perform an independent medical assessment of the reported case.

### **5.6 ADVERSE EVENTS THAT OCCUR AFTER THE ADVERSE EVENT REPORTING PERIOD**

*The Sponsor should be notified if the investigator becomes aware of any serious adverse event that occurs after the end of the adverse event reporting period (defined as 28 days [see Section 5.3.1] after the final dose of study drug), if the event is believed to be related to prior study drug treatment. These events should be reported through use of the Adverse Event eCRF. However, if the EDC system is not available, the investigator should report these events directly to the Sponsor or its designee, either by faxing or by*

*scanning and emailing the paper Clinical Trial Serious Adverse Event/Adverse Event of Special Interest Reporting Form using the fax number or email address provided to investigators.*

## **5.7 EXPEDITED REPORTING TO HEALTH AUTHORITIES, INVESTIGATORS, INSTITUTIONAL REVIEW BOARDS, AND ETHICS COMMITTEES**

To determine reporting requirements for single adverse event cases, the Sponsor will assess the expectedness of these events using the following reference document(s):

- Vemurafenib IB
- Local prescribing information for Zelboraf® (vemurafenib)
- Vemurafenib (Zelboraf) Core Data Sheet

The Sponsor will compare the severity of each event and the cumulative event frequency reported for the study with the severity and frequency reported in the applicable reference document.

Reporting requirements will also be based on the investigator's assessment of causality and seriousness, with allowance for upgrading by the Sponsor as needed.

## **6. STATISTICAL CONSIDERATIONS AND ANALYSIS PLAN**

There is no formal hypothesis testing in this extension (rollover) study. Data will be collected and reported descriptively for all study endpoints.

The final analysis of this study will be performed when all patients have been followed up per protocol (see Section 3.2 and Section 3.3).

### **6.1 SUMMARIES OF CONDUCT OF STUDY**

A clinical study report will be written and distributed to Health Authorities as required by applicable regulatory requirements. Enrollment, eligibility violations, and study treatment administration will be summarized. Patient disposition will be summarized and include whether treatment was completed or discontinued early and the reason for early treatment discontinuation.

### **6.2 EFFICACY ANALYSIS**

No protocol-specific efficacy analysis will be performed for this study.

### **6.3 SAFETY ANALYSIS**

The safety analysis will include all patients who receive at least one dose of vemurafenib.

Incidence, nature, and intensity (severity) of adverse events and serious adverse events, graded according to NCI CTCAE v4.0 will be summarized.

Changes in vital signs (blood pressure, pulse, temperature), ECGs, and clinical laboratory results during the course of study will be summarized.

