### **3.2 LENGTH OF STUDY**

Treatment will continue until disease progression (as defined by investigator) or as long as the patient is deriving clinical benefit, as assessed by investigator, if treated beyond progression (case-by-case decision discussed and approved by the Medical Monitor), death, withdrawal of consent, unacceptable toxicity, loss to follow-up, or decision of the Sponsor to terminate the study, whichever occurs first.

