##### **Disease-Specific Inclusion Criteria**

1. *BRAF*V600 mutation-positive malignancy
2. Prior eligibility for and received study treatment on an antecedent vemurafenib protocol
3. Ability to begin treatment in the extension (rollover) protocol within 15 days following the last day of the study in the antecedent protocol

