## **4.5.2 Timing of Study Assessments**

### **4.5.2.1 Screening/Baseline and Pretreatment Assessments**

Written informed consent for participation in the study must be obtained before performing any study-specific baseline tests or evaluations. Informed Consent Forms for enrolled patients and for patients who are not subsequently enrolled will be maintained at the study site.

The investigator must maintain a patient Enrollment and Identification Code List.

Results from the study completion visit or other prior visit assessment in the antecedent protocol may be used as screening/baseline for this extension (rollover) study, if within time intervals, as specified in this section and [Appendix 1](#); screening/baseline is combined into one visit.

Under no circumstance will patients be permitted to re-enroll in the study if they have previously enrolled in this study and completed/discontinued treatment as specified.

All required screening/baseline procedures including data collection or transfer from the antecedent study must be performed after the patient has provided informed consent within a maximum window of 15 days from the last *dose of study drug* in the antecedent study to until the *first dose* of treatment in this extension (rollover) study, or as specified in Section [4.5.1](#) and [Appendix 1](#) for specific assessments.

All patients will be closely monitored for safety and tolerability during all cycles of therapy and at the study completion visit. After signing the Informed Consent Form, all adverse events and serious adverse events (including serious adverse events due to invasive procedures required for the study such as biopsies) will be collected. Patients will be assessed for adverse events prior to each subsequent cycle and as necessary throughout the study. All adverse events will be recorded until 28 days after the last dose of study treatment or until initiation of another anti-cancer therapy, whichever occurs first.

Visits are based on a 28-day cycle. If the timing of a protocol-mandated procedure coincides with a holiday or another scheduling conflict that precludes the visit, the visit should be scheduled within  $\pm 3$  days of the date in question, which may be earlier or later.

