### **5.3.1 Adverse Event Reporting Period**

Investigators will seek information on adverse events at each patient contact. All adverse events, whether reported by the patient or noted by study personnel, will be recorded in the patient's medical record and on the Adverse Event eCRF.

After informed consent has been obtained but prior to initiation of study drug, only serious adverse events caused by a protocol-mandated intervention should be reported (e.g., serious adverse events related to invasive procedures such as biopsies).

After initiation of study drug, all adverse events, regardless of relationship to study drug, will be reported until 28 days after the last dose of study treatment or until initiation of another anti-cancer therapy, whichever comes first.

*Instructions for reporting adverse events that occur after the adverse event reporting period are provided in Section 5.6.*

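### Section 6.3 reports AE incidence without time at risk and without separating new events from AEs carried over from the antecedent study

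*Combined protocol and SAP*

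**What the plan says.** **Analysis (Sections 6, 6.1, 6.3; Section 6.3 is repeated in the synopsis).** The population is defined by "The safety analysis will include all patients who receive at least one dose of vemurafenib", and the measure by "Incidence, nature, and intensity (severity) of adverse events and serious adverse events, graded according to NCI CTCAE v4.0 will be summarized". Section 6.1 adds "Enrollment, eligibility violations, and study treatment administration will be summarized", together with disposition, as a description of study conduct. Section 6 says that reporting is descriptive and nothing is tested. It names no person-time denominator, exposure-adjusted rate or time-to-event summary.

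**Length of observation.** Under Section 3.2 treatment lasts until progression, "or as long as the patient is deriving clinical benefit, as assessed by investigator, if treated beyond progression", or until another stopping reason. Under Section 5.3.1, AEs after the first dose "will be reported until 28 days after the last dose of study treatment or until initiation of another anti-cancer therapy", whichever is first.

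**Prior exposure.** Section 4.1.1 asks only for "Prior eligibility for and received study treatment on an antecedent vemurafenib protocol", with no minimum or maximum. Section 4.5.2.2 provides for patients who arrive with 17 or more cycles.

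**AEs present at entry.** Section 5.3 has AEs unresolved at enrollment entered on this study's AE eCRF under the antecedent onset date. Section 5.3.5.8 sends conditions present at baseline to the medical history eCRF and makes them AEs only if they worsen.

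**The concern.** Describing safety and tolerability during continued treatment is the study's only data objective (Section 2.2); the primary objective is access to drug, and there is no efficacy analysis. The AE table is therefore the main scientific output.

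Two things blur it. First, a percentage of dosed patients over unequal and unlimited follow-up is a valid count, but it cannot be read as a risk unless time at risk is shown. Two cohorts with the same underlying rate can show very different percentages.

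Second, every patient enters from treatment on a vemurafenib protocol, so ongoing AEs at entry are to be expected. They sit in the same AE dataset as new events, and no analysis rule says whether they count towards incidence. Two programmers who both follow the text could produce different tables.

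**Working it through.** The documents give no sample size, event count or power, so there is no design figure to reproduce. The hazards and carry-over shares below are assumptions.

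**1. Length of stay.** Under a constant hazard h, crude incidence after t years is 1 − exp(−h·t). With 28-day cycles, 6 cycles = 168/365.25 = 0.460 years and 39 cycles = 1092/365.25 = 2.990 years.

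| h per year (assumed) | 6 cycles | 39 cycles | Rate per 100 patient-years |
|---|---|---|---|
| 0.05 | 2.3% | 13.9% | 5 in both |
| 0.20 | 8.8% | 45.0% | 20 in both |
| 0.50 | 20.5% | 77.6% | 50 in both |

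The equal rates follow from the constant-hazard assumption and are not a finding. The protocol's own background shows the same dependence: Section 1.2.1.5 gives neutropenia as 6 cases per 1000 person-years and as 0.6%. Those agree at one year, since 1 − exp(−0.006) = 0.598%. Under a constant hazard the same rate gives 0.28% at 6 cycles and 1.78% at 3 years. This is arithmetic only, because the section says neutropenia tends to come early.

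**2. Carried-over AEs.** Let c be the share entering with the event ongoing, and take h = 0.20 for one year, so new-onset risk is 1 − exp(−0.20) = 18.1%. Counting every record gives c + (1 − c)·0.181. Counting new onset over all dosed patients gives (1 − c)·0.181.

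| c (assumed) | All records | New onset only |
|---|---|---|
| 0% | 18.1% | 18.1% |
| 10% | 26.3% | 16.3% |
| 30% | 42.7% | 12.7% |
| 50% | 59.1% | 9.1% |

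Even the new-onset column falls with c, because patients who already have the event stay in the denominator. At c = 30%, 12.7/70 returns 18.1%. Hence the need for an at-risk denominator.

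**3. The two recording rules side by side.** An AE that began in the antecedent study and is unresolved at enrollment falls under Section 5.3, which records it as an AE with its old onset date. It is also present at baseline, so Section 5.3.5.8 would record it as an AE only on worsening. Section 6.3 does not choose between them.

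**4. Early-onset events: cuSCC.** Section 1.2.1.5 gives an incidence of about 20% and a median of 7–8 weeks to first appearance. Assume exponential onset among that 20%, S(w) = 2^(−w/m) with m = 7 to 8 weeks. For a patient with no cuSCC after w weeks of prior exposure, the chance of a first one in the next 24 weeks is 0.2[S(w) − S(w+24)] / [0.8 + 0.2·S(w)].

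| Antecedent cycles (weeks) | First cuSCC in next 24 weeks |
|---|---|
| 2 (8) | 9.2–9.7% |
| 4 (16) | 4.4–5.1% |
| 8 (32) | 0.9–1.3% |
| 17 (68) | under 0.1% |

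As a check, 1 − S(16) = 75–79%, which fits the statement in Section 5.1.1 that most SCCs came within 16 weeks. The gradient lies in the first few cycles.

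A single rate does not cure this. With w = 8 and m = 7.5, the expected first-event rate is 22 per 100 patient-years over 24 weeks of follow-up and 4.0 over 156 weeks. So time at risk has to stand beside each rate.

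**The case against.** The strongest reply is that this is a single-treatment access study with no hypothesis test, that percentages are honest counts, and that the material is already there: Section 6.1 summarizes treatment administration, Section 5.3.1 fixes the reporting window, and the antecedent onset dates make carried-over events separable. It can add that Section 5.3.5.8 is a general rule about medical conditions, and Section 5.3 the specific one about AEs.

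Most of this is right and it limits the weight of the point. What remains is that separable is not separated: no analysis rule uses the onset date, and Section 6.1 does not tie exposure to the AE tables. Reading one recording rule as overriding the other is reasonable, but the text does not say so.

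Three stronger readings are tempting and not supported:

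- **That skin surveillance differs lastingly by prior exposure.** A reader might infer this from the separate schedule for patients with 17 or more antecedent cycles. Section 4.5.1.9 moves every patient still on treatment to every third cycle from Cycle 18, so the schedules converge.
- **That AEs must be split at 17 antecedent cycles.** That number sets visits; it is not a risk boundary. At 68 weeks it lies far beyond the 2 to 4 cycles in which cuSCC risk is concentrated, so the lower group would pool nearly the whole gradient.
- **That pre-dose collection is part of this problem.** Section 4.5.2.1 collects "After signing the Informed Consent Form, all adverse events and serious adverse events", whereas Section 5.3.1 says that before the first dose "only serious adverse events caused by a protocol-mandated intervention should be reported". That is a real inconsistency, but a separate one about data capture, and it says nothing about time at risk.

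**Conclusion.** The point holds as an improvement that should be made. Section 6.3 lets crude incidence vary with length of stay and leaves open whether AEs with onset before this study count as incident. The second part rests on the text alone. The sizes in the first part rest on assumed hazards, and the 42.7% versus 12.7% contrast on an assumed carry-over share; the documents give neither the distribution of stay nor that of prior exposure.

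The cuSCC figures use the protocol's own incidence and median, but an assumed onset shape, and they cover first-ever events only. About a third of affected patients had more than one occurrence, at a median of 6 weeks apart (Section 1.2.1.5), so a table that admits patients with an earlier, resolved cuSCC would show more events than the model.

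A reader might infer that the planned percentages are wrong. They are not; they are incomplete. The effect is on how a descriptive safety objective can be read, and no error rate is involved.

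**What to change.** In Section 6.3:

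1. Keep the percentages, but base them on new-onset AEs (onset on or after the first GO28399 dose) and on carried-over AEs that worsen, with the two shown separately. List other carried-over AEs apart.
2. Reconcile Section 5.3 with Section 5.3.5.8, so that an AE unresolved at enrollment has one recording rule.
3. Report total patient-years in GO28399. For common AEs, SAEs and AEs of special interest, add first new-onset events per 100 patient-years at risk, with an exact Poisson 95% CI and median time at risk. Time runs from the first GO28399 dose to the first such event or the end of the Section 5.3.1 reporting period, among patients without an unresolved record of that event at first dose.
4. For cuSCC, state whether patients with an earlier, resolved cuSCC are in the at-risk group, and show first-ever and recurrent events separately where antecedent data allow.
5. If prior exposure is described, report its distribution or use early-exposure cut points where numbers allow.

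The cost is a few extra tables from dosing and onset dates already collected; no visit or procedure is added. First-ever cuSCC status and prior exposure need antecedent records. The tables will be sparse for rare events. With no events the exact upper limit is −ln(0.025) = 3.689 events, i.e. 3.7 per 100 patient-years on 100 patient-years, 7.4 on 50 and 14.8 on 25. That is a reason to keep any subdivision small.

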## **7. DATA COLLECTION AND MANAGEMENT**

### **7.1 DATA QUALITY ASSURANCE**

Roche will be responsible for data management of this study, including quality checking of the data. Data entered manually will be collected via EDC with use of eCRFs. Sites will be responsible for data entry into the EDC system. In the event of discrepant data, Roche will request data clarification from the sites, which the sites will resolve electronically in the EDC system.

Roche will produce an EDC Study Specification document that describes the quality checking to be performed on the data. Central laboratory data will be sent directly to Roche, with use of Roche's standard procedures to handle and process the electronic transfer of these data.

eCRFs and correction documentation will be maintained in the EDC system's audit trail. System backups for data stored at Roche and records retention for the study data will be consistent with Roche's standard procedures.

### **7.2 ELECTRONIC CASE REPORT FORMS**

eCRFs are to be completed using a Sponsor-designated EDC system. Sites will receive training and have access to a manual for appropriate eCRF completion. eCRFs will be submitted electronically to Roche and should be handled in accordance with instructions from Roche.

All eCRFs should be completed by designated, trained site staff. eCRFs should be reviewed and electronically signed and dated by the investigator or a designee.

At the end of the study, the investigator will receive patient data for his or her site in a readable format on a compact disc that must be kept with the study records. Acknowledgement of receipt of the compact disc is required.

### **7.3 SOURCE DATA DOCUMENTATION**

Study monitors will perform ongoing source data verification to confirm that critical protocol data (i.e., source data) entered into the eCRFs by authorized site personnel are accurate, complete, and verifiable from source documents.

Source documents (paper or electronic) are those in which patient data are recorded and documented for the first time. They include but are not limited to hospital records, clinical and office charts, laboratory notes, memoranda, patient-reported outcomes, evaluation checklists, pharmacy dispensing records, recorded data from automated instruments, copies of transcriptions that are certified after verification as being accurate

and complete, microfiche, photographic negatives, microfilm or magnetic media, X-rays, patient files, and records kept at pharmacies, laboratories, and medico-technical departments involved in a clinical trial.

Before study initiation, the types of source documents that are to be generated will be clearly defined in the Trial Monitoring Plan. This includes any protocol data to be entered directly into the eCRFs (i.e., no prior written or electronic record of the data) and considered source data.

Source documents that are required to verify the validity and completeness of data entered into the eCRFs must not be obliterated or destroyed and must be retained per the policy for retention of records described in Section 7.5.

To facilitate source data verification, the investigators and institutions must provide the Sponsor direct access to applicable source documents and reports for trial-related monitoring, Sponsor audits, and IRB/EC review. The investigational site must also allow inspection by applicable health authorities.

